13.1.6 Color Fundus Photography (CFP)

CFP will be performed in study eye and contralateral eye at the time points specified in the Schedule of Assessments (refer to protocol).

Separate listing will be presented for the same.

13.1.7 Fundus Autofluorescence

Fundus Autofluorescence will be performed at Visit 8 in both eyes. Listing will be presented for the same.

13.1.8 Indirect Ophthalmoscopy

Ophthalmic Exam will be performed via indirect ophthalmoscopy at baseline and at other times according to the Schedule of Assessments (please refer to Protocol).

The following parameters will be assessed and summarized as described in section 3.1 (continuous/categorical descriptive analysis) in study eye and fellow eye:

- Posterior Vitreous Detachment
- C/D Ratio
- Macula
- Vessels
- Periphery

All grading assessments of different eye structures will be summarized descriptively by abnormalities, cohort and study visit for both eyes (categorical descriptive analysis as mentioned in section 3.1).

All data recorded on the eCRF page 'Indirect Ophthalmoscopy (Retinal Exam)' will be listed.

In addition, separate by-patients listing will be provided for pre- and post-surgery of the retinal examination.

13.1.9 Slit Lamp Biomicroscopy

Biomicroscopy will be performed with a slit-lamp to examine the anterior and posterior chambers of the eye. The examination will include following assessments as per Schedule of Events please refer to the Protocol).

- Anterior Segment
 - Anterior Chamber Cell
 - Anterior Chamber Flare
- Posterior Segment
 - Optic Disc
 - o Vitreous Cell
 - Vitreous Haze
- Lens Status
 - Nuclear Sclerosis
 - Cortical Cataract
 - Posterior subcapsular cataract

All grading assessments of different eye structures will be summarized descriptively by abnormalities, cohort and study visit for both eyes (categorical descriptive analysis as mentioned in section 3.1).

Listing will be provided for the same.

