1.4 Potential Risks and Benefits

1.4.1 Potential Risks of Study Product

There could be a risk of an adverse reaction to the ONL1204 drug product or vehicle.

Although unlikely, potential risks include:

- Intraocular inflammation
- Elevated intraocular pressure
- Visual loss
- Retinal cell death
- Less favorable surgical outcome following repair
- Systemic adverse reaction

Patients will be carefully monitored after vitreous tap and intravitreal injection of ONL1204, with multiple post procedure visits with the investigator. At these visits, visual acuity will be assessed, intraocular pressure measured, the eyes examined according to assessments listed in 6.4.2, and any adverse events (AEs) reviewed. Based on these assessments, additional visits may be scheduled at investigator discretion. This close monitoring for inflammation, infection, and changes in vision will help reduce associated risks.

There is a remote risk of systemic adverse reaction in response to intravitreal injection of ONL1204. This risk is greatly mitigated by the study molecule's long half-life in vitreous (most drug stays in the eye until surgery) and extremely short half-life in plasma. Patients will undergo clinical blood testing, with assessment of complete blood count, renal function tests and hepatic function tests to monitor for any such systemic adverse reactions.

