4.2 Dose Limiting Criteria and Maximum Tolerated Dose

4.2.1 Dose Limiting Criteria

Dose limiting toxicity, if observed, will be declared by the SRC, based on their review of the relevant clinical information.

Determination of dose limiting toxicity will include consideration of the following events:

- 1. Ocular inflammation increases by 2 units from pre-injection on the Standardization of Uveitis Nomenclature (SUN) grading scale for aqueous cell or vitreous haze, secondary to inflammation and not the drug formulation itself, identified post-injection of ONL1204 and prior to retinal reattachment surgery;
- 2. Sustained elevation of IOP characterized as > 30 mmHg for 3 consecutive days, postinjection of ONL1204 and prior to retinal reattachment surgery, despite pharmacologic therapy;
- 3. Reduction in visual acuity from baseline after injection of ONL1204 and prior to retinal reattachment surgery, that in the opinion of the investigator is likely due to the investigational product and results in a:
 - a) Decrease in visual acuity from 20/200 or 20/400 to light perception without progression of the underlying retinal detachment; or
 - b) Decrease in visual acuity from baseline to no light perception.
- 4. Any serious adverse event (SAE) that occurs within the first 14 days following ONL1204 injection that, in the opinion of the investigator, is related to ONL1204.

Page 23 of 52

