4.3 Schedule of Assessments

Table 4-1 Schedule of Study Procedures and Assessments

Study Visit	Visit 1 Day 1 Baseline ² / Injection			Visit 2 Day 2 (¹ ,	Visit 3 (Day 4 +)	Visit 4	Visit 5	Visits 6, 7	Visit 8	Unscheduled Visit(s)
				1 day Post- Injection	3 + days Post- Injection) Day of Surgery (Vitrectomy) ³	1 Day Post- Surgery	14 Days (±4 days) Post- Surgery	Weeks 6, 9 (±7 days)	Week 24 (±14 days) Exit or early termination	
Assessment	Pre- Injection	Study Drug IVT	Post- Injection							
Informed Consent	X									
Medical History	X									
Demographics	X									

³ All Visit 3 procedures are to be performed before vitrectomy.

Note: Screening procedures are in red.

Abbreviations: AE = Adverse event; ETDRS = Early Treatment Diabetic Retinopathy Study; IOP = Intraocular pressure; PK = Pharmacokinetic;

Post-op = Postoperative; OU = Both eyes; SD OCT = Spectral Domain Optical Coherence Tomography; SE = Study eye; UA = Urine analysis.

¹ IOP > 30 mmHg requires consecutive daily visits until resolved or vitrectomy. Visits between visit 2 and 3 may be added per investigator's discretion.

² All baseline procedures to be done before injection, except blood draw for ONL1204 levels and PK sample (may be drawn with clinical laboratory evaluations, and 1 hour [\pm 15 minutes] after injection), and AE reporting, (pre- and post-injection). If injection is scheduled for early morning, baseline procedures can be done the day before surgery.

Page 25 of 52

Study Visit	Visit 1 Day 1			Visit 2 Day 2 (¹ ,	Visit 3 (Day 4 +)	Visit 4	Visit 5	Visits 6, 7	Visit 8	Unscheduled Visit(s)
	Bas	eline ² / Inje	ction	1 day Post- Injection	3 + days Post- Injection) Day of Surgery (Vitrectomy) ³	1 Day Post- Surgery	14 Days (±4 days) Post- Surgery	Weeks 6, 9 (±7 days)	Week 24 (±14 days) Exit or early termination	
Assessment	Pre- Injection	Study Drug IVT	Post- Injection							
Concomitant Medications	X			X	X	Х	X	X	Х	Х
Vital Signs	X			X	Х	Х	X	Х	Х	Х
Height and weight	Х									
Pregnancy Test (UA) (females only)	X								Х	
ETDRS Best Corrected Visual Acuity	OU			OU				OU	OU	SE ⁴
Clinical Laboratory Evaluation	X		X		X				X	

Note: Screening procedures are in red

Abbreviations: AE = Adverse event; ETDRS = Early Treatment Diabetic Retinopathy Study; IOP = Intraocular pressure; PK = Pharmacokinetic; Post-op = Postoperative; OU = Both eyes; SD OCT = Spectral Domain Optical Coherence Tomography; SE = Study eye; UA = Urine analysis. ⁴ OU if clinically indicated.

Page 26 of 52

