2.1.1 Primary objective

The primary objective will be to determine the Maximum Tolerated Dose (MTD) of ONL1204 and select doses for Phase 2. Determination of this will be through review of the parameters measured in the Schedule of Assessments, as well as adverse event (AE) reports.

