For PK concentration data, the number of non-missing values, number of below limit of quantification (BLQ) values, arithmetic mean, standard deviation, median, minimum, maximum, coefficient of variation (CV%), geometric mean and geometric coefficient of variation (geo CV%) values will be presented. For the calculation of summary statistics, unrounded data will be used and reported to three significant figures except for n, n BLQ, and CV% which will be presented to the nearest integer and one decimal place, respectively.

For PK parameters data, the number of non-missing values, arithmetic mean, standard deviation, median, minimum, and maximum values will be presented. Individual PK parameters will be presented to three significant figures except for T_{max} which will be presented to two decimal places.

- Categorical variables: Descriptive statistics will include counts and percentages per category. The denominator in all percentage calculations will be the number of participants in the relevant analysis population with non-missing data, unless specifically stated otherwise. Percentages will be displayed to one decimal place. Proportions will be displayed to 3 decimal places.
- Unscheduled assessments: Only values collected at scheduled study visits/time points will be presented in summary tables. If a repeat assessment was performed, the result from the original assessment will be presented as the result at the specific visit/time point. All collected data will be included in the data listings.

- Assessment windows: All assessments will be included in the data listings and no visit windows will be applied to exclude assessments that were performed outside of the protocol specified procedure windows.
- Result display convention: Results will be center aligned in all summary tables and listings. Participant identifiers visit and parameter labels may be left-aligned if required.
- Date and time display conventions: The following display conventions will be applied in all outputs where dates and/or times are displayed:

Date only: YYYY-MM-DD

Date and time: YYYY-MM-DD HH:MM

If only partial information is available, unknown components of the date or time will be presented as 'NK' (not known), i.e., '2016-NK-NK'. Times will be reported in military time.

Key Definitions

The following definitions will be used:

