- Baseline: The baseline value is defined as the last available valid (quantifiable continuous or categorical value), non-missing observation for each participant prior to first study drug administration. Repeat and unscheduled assessments will be included in the derivation of the baseline values.
- Change from Baseline: The change from baseline value is defined as the difference between the result collected/derived at a post-baseline visit/time point and the baseline value.

The change from baseline value at each post-baseline visit/time point will be calculated for all continuous parameters using the following formula:

Change from Baseline Value = Result at Visit/Time Point – Baseline Value

The change from baseline value will only be calculated if the specific post-baseline visit/time point result and the baseline value for the parameter are both available and will be treated as missing otherwise.

• Study day: The study day of an event is defined as the relative day of the event starting with the date of the first study drug administration (reference date) as Day 1 (there will be no Day 0).

The study day of events occurring before the first study drug administration will be calculated as:

Study Day = (Date of Event - Date of First Study Drug Administration)

For events occurring on or after Day 1, study day will be calculated as:

Study Day = (Date of Event - Date of First Study Drug Administration) + 1

Study days will only be calculated for events with complete dates and will be undefined for events that are 'Ongoing' at the end of the study.

Relative days compared to an alternative reference point will be calculated similarly, but the alternative starting reference start date will be used instead of the date of the first study drug dosing.

- Prior Medications: Prior medications are defined as any medication where the use was stopped prior to the first administration of the study medication.
- Concomitant Medications: Concomitant medications are defined as any medication (other than the study drug) that was used at least once after the first administration of the study drug. Medications that were stopped on the same date as the first study drug administration will be defined as concomitant medications. If a clear determination cannot be made (partial medication end dates) the medication will be classified as concomitant.

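### The slit-lamp summary does not link an eye's grade to its pre-injection grade and omits added visits, so the end-of-study comparison of doses can understate peak inflammation before surgery

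*SAP*

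**What the plan says.** - **The risk.** Protocol 1.4.1 lists "Intraocular inflammation" first among the potential risks of the product.
- **The event.** Criterion 1 in Protocol 4.2.1 reads: "Ocular inflammation increases by 2 units from pre-injection on the Standardization of Uveitis Nomenclature (SUN) grading scale for aqueous cell or vitreous haze". It applies to a rise "identified post-injection of ONL1204 and prior to retinal reattachment surgery". The safety review committee (SRC) considers the criteria and declares any dose-limiting toxicity.
- **The objective.** SAP 2.1.1: "The primary objective will be to determine the Maximum Tolerated Dose (MTD) of ONL1204 and select doses for Phase 2". The primary endpoint is the safety profile.
- **The summary of grades.** SAP 13.1.9 collects anterior chamber cell and vitreous haze, among other items, and says: "All grading assessments of different eye structures will be summarized descriptively by abnormalities, cohort and study visit for both eyes". It treats them as categorical, which under SAP section 3 means counts and percentages. It also promises a listing.
- **Change from baseline.** SAP section 3: "The change from baseline value at each post-baseline visit/time point will be calculated for all continuous parameters".
- **Unscheduled visits.** SAP section 3: "Only values collected at scheduled study visits/time points will be presented in summary tables". Footnote 1 to Protocol Table 4-1 says: "Visits between visit 2 and 3 may be added", at the investigator's discretion.
- **Planned outputs.** Table 14.3.6.5 is the only slit-lamp table, and its title mentions no change or shift. The only shift tables are for hematology and chemistry. No table counts dose-limiting events. Individual examinations go to Listing 16.2.11.9.

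**The concern.** The protocol describes the inflammation of interest as a change within one eye, inside a short window. The SAP describes the same data as separate cross-sections by visit. Two pieces of information drop out of the table.

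1. **The link.** Counts at baseline and counts at a later visit do not say which eye moved from which grade.
2. **The added visits.** After the injection day, the scheduled visits before surgery are Visit 2 (Day 2) and at most Visit 3 (the day of surgery, 3 or more days after injection). An extra visit between them may well be prompted by how the eye looks, and its grade enters no slit-lamp table.

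At stake is the final report's comparison of doses on the first-named risk, which supports the MTD and the choice of Phase 2 doses.

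**Working it through.** The documents give no sample size or precision figure bearing on this point, so there is nothing to reproduce. There are three checks.

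**1. Criterion against table**

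| Feature | Protocol 4.2.1, criterion 1 | SAP 13.1.9 and Table 14.3.6.5 |
|---|---|---|
| Quantity | Change from pre-injection | Grade at each visit |
| Unit | One eye | Cohort counts |
| Window | Injection to surgery | Each scheduled visit, before and after surgery |
| Added visits | Not excluded | Excluded |

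Laboratory values, vital signs and BCVA letters all get a change from baseline in the SAP. The criterion 1 variables do not.

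**2. What unlinked counts can determine**

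Inputs: 4 patients per cohort (Protocol study schematic), one pre-injection and one later visit. Assumption: whole-number grades 0 to 3, repeated for 0 to 4, because the documents do not print the SUN levels.

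For each pair of count sets, every matching of eyes was tried. The smallest and largest possible numbers of eyes with (later grade − pre-injection grade) ≥ 2 were recorded. The number is undetermined when the two differ. There are C(7,4) = 35 count sets for grades 0 to 3, so 35 × 35 = 1225 pairs, and C(8,4) = 70 for grades 0 to 4, so 70 × 70 = 4900 pairs.

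| Highest pre-injection grade in the cohort | Undetermined, grades 0–3 | Undetermined, grades 0–4 |
|---|---|---|
| 0 | 0 of 35 | 0 of 70 |
| 1 | 57 of 140 (41%) | 102 of 280 (36%) |
| Any | 649 of 1225 (53%) | 3040 of 4900 (62%) |

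Examples:
- Pre-injection 0, 0, 0, 1 and later 0, 0, 0, 2: 0 or 1 rise of 2 units.
- Pre-injection 0, 0, 1, 1 and later 0, 0, 2, 2: 0, 1 or 2 rises.
- Pre-injection 0, 0, 0, 0 and later 0, 0, 1, 2: exactly 1 rise.

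These are shares of possible patterns, each counted once, not probabilities. The last row includes cohorts with high pre-injection grades, which exclusion criterion 3 (no intraocular inflammation in either eye) should keep out. The first two rows are the relevant ones.

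**3. What the scheduled-only rule removes**

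An invented eye: pre-injection 0, Visit 2 grade 0, added visit 2+, Visit 3 grade 1+.
- Largest rise over all examinations: 2 − 0 = 2 units.
- Largest rise over scheduled examinations: 1 − 0 = 1 unit.

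This loss occurs even when every pre-injection grade is 0.

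**The case against.** The case on the other side is substantial, and most of it stands.

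- **The listing has the data.** SAP section 3 puts all collected data in the listings, so Listing 16.2.11.9 includes added visits. With 4 patients per cohort and 16 in all, a rise can be read by eye. This stands. What a listing does not give is a count by dose.
- **A real rise should be an adverse event.** Protocol 7.11 makes clinically relevant deterioration in ocular findings an AE. The TEAE tables are not limited to scheduled visits, so an event found at an added visit would be counted by cohort. This stands. Those tables report preferred term, severity and relationship, however, not the change in grade that criterion 1 uses.
- **Escalation does not rest on this table.** The SRC declares dose-limiting toxicity from its own review during the study, and Table 14.3.6.5 is produced at the end. This stands.
- **Exclusion 3 makes most pre-injection grades low.** This largely stands: with all baselines at 0, scheduled-visit counts determine the number of 2-unit rises. The exclusion names no grade, though, and does nothing for peaks at added visits.
- **A count of rises is not criterion 1.** The criterion also requires the rise to be attributed to inflammation rather than to the formulation. This stands and shapes the fix.
- **The SAP already exceeds the protocol.** Protocol 9.3.1 gives slit-lamp grades no analysis of their own; 9.3.1.8 requires other safety data only to be listed, with summaries optional. True, but once the SAP tabulates the grades, the table should show the change that the protocol itself names.

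**Conclusion.** The point holds as a gap in the end-of-study tables. Table 14.3.6.5 does not link an eye's grade to its pre-injection grade and leaves out grades from added visits, so it can understate peak inflammation before surgery when doses are compared. The change is worth making, and modest in weight.

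Three stronger readings are tempting, and the documents do not support them.
- *No table could reveal such a rise.* By-visit counts do reveal it at a scheduled visit when all pre-injection grades are 0, and the TEAE tables should carry a clinically relevant one.
- *The MTD or the escalation decisions are compromised.* The SRC decides on its own data review.
- *A cohort would be reported as 0/4 when the truth is 1/4.* The SAP plans no such row, and the example eye is invented. Its slit-lamp row would not be flat either, since it shows 1+ at Visit 3.

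The size in practice depends on how many visits are added and when grades peak, and the documents give neither. The verdict assumes that the grades collected under SAP 13.1.9 are on the scale named in criterion 1. The SAP does not name SUN, and the eCRF is not in the documents.

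**What to change.** Add to SAP 13.1.9 and the table list one table by cohort, for the study eye only:

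- pre-injection grade (SAP baseline definition, which already covers categorical values) against the worst grade over all scheduled, repeat and unscheduled examinations from injection to vitrectomy;
- separately for anterior chamber cell and for vitreous haze;
- n/N with an increase of 2 or more units, using the grade categories as collected on the eCRF;
- a footnote saying that this is a descriptive count, not a count of SRC-declared dose-limiting toxicities, because criterion 1 also needs a judgement of cause.

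State that the table is an exception to the scheduled-visits-only rule. Keep the by-visit counts as they are. No change table after surgery is needed for this purpose, because the criterion 1 window ends at surgery.

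The cost is one derived table and that exception. No visit, assessment or clinical criterion changes. If the eCRF grades are not coded in SUN units, the SAP should also state how they correspond.

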13.1.10 Intraocular Pressure (IOP)

IOP measurements will be done using applanation tonometry (either Goldmann (standard preferred method) or Tonopen® (use only if required)). For any given participant, the same IOP procedures will be followed for the entire duration of the study. Below measurement will be taken for both eyes.

• IOP (mmHg)

Summary of IOP measured for both eyes will be presented as per visit.

13.1.11 Pin Hole Visual Acuity

Pin Hole Visual Acuity measurements (taken at 1 Day Post-Surgery only) will be summarized using descriptive statistics described in section 3.1 for continuous data by cohort by LogMAR Score.

13.1.12 Contrast Sensitivity Testing

Contrast Sensitivity Testing measurements will be measured at the time points specified in the Schedule of Assessments (refer to protocol). Scores will be summarized for both the eyes. Results will be reported in log values.

13.1.13 Farnsworth D15 Color vision test

Farnsworth D15 color vision measurements will be assessed in both study eye and fellow eye. Separate listing will be provided.

13.1.14 Spectral Domain Optical Coherence Tomography (SD-OCT)

SD-OCT will be performed in study eye and contralateral eye at the time points specified in the Schedule of Assessments (refer to protocol). Measurements of retinal thicknesses and volumes based on determinations relying on typical retinal layers as identified by SD-OCT will be calculated. Specifically, the following results will be presented from all assessments except for the pre-injection baseline measurement. The results for the parameters below will be summarized as described in section 3.1 (continuous descriptive analysis):

- Average thickness central 1 mm (central subfield thickness)
- Average thickness central 3 mm
- Average thickness central 6 mm
- Total centerpoint thickness
- Central subfield volume
- Macular volume
- Subretinal fluid thickness at the foveal center

The following parameters will be summarized as described in section 3.1 (categorical descriptive analysis) for the collected categories with each parameter:

- Vitreomacular traction deforming the fovea
- Intraretinal fluid (cystoid macular edema)
- Epiretinal membrane
- Epiretinal membrane with deformation in the center 1 mm
- Anomaly

The results from the analyses of the parameters listed in this section above will be prepared by ONL and presented as an addendum to the tables, listings, and figures report.

The following parameters with continuous numerical results will also be obtained from all assessments except for the Screening measurement. These results may be analyzed and reviewed, with or without descriptive statistics, internally. The results for the following parameters will be available for the central 1 mm, 3 mm, and 6 mm of the scan, as well as the volume of the central 1 mm region.

- Boundaries ILM to inner aspect of ONL
- Boundaries inner aspect of ONL to Bruch's Membrane
- Boundaries ELM to Bruch's Membrane

The following parameters with categorical results will also be obtained from all assessments except for the Screening measurement. These results may be analyzed and reviewed, with or without categorical descriptive statistics, internally.

- Intraretinal fluid in the central subfield
- Intraretinal fluid at the foveal center
- Subretinal fluid in the center 3 mm
- Subretinal fluid in the center 1 mm
- Subretinal fluid at the foveal center
- Anomaly details
 - Retinal pigment epithelium (RPE) elevation, RPE atrophy, outer retinal lucency
 - o Potential risk management
 - o Other

The results from the analyses of the parameters identified in this section above will be included in the addendum to the tables, listings, and figures report only if deemed pertinent and potentially informative by expert review.

Pregnancy Test Results

All information related to pregnancy testing (urine) and contraception status will be presented in the byparticipant data listings.

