4.1 Overview of Study Design

Sixteen patients will be enrolled in 4 ascending dose groups.

After signing informed consent and meeting all eligibility criteria, patients will undergo a vitreous tap for cytokine and other potential molecular biomarker analysis followed by a single intravitreal injection of ONL1204. This will occur on the day of diagnosis (Day 1). Safety visits will be conducted 1 day post-injection and per Investigator's discretion until Visit 3. At Visit 3 (3+ days post-injection, in accordance with standard of care) patients will undergo surgical repair of their retinal detachment with vitrectomy (with or without scleral buckling) and gas or oil tamponade. At the time of surgery, an undiluted vitreous sample will be collected for pharmacokinetic and pharmacodynamics analyses, and an aqueous sample will be collected for pharmacodynamic analysis. Additional safety visits will be conducted 1 day post-surgery, 14 (+4 days) days post-surgery, Weeks 6, 9 (\pm 7 days each), and Week 24 (\pm 14 days; study exit).

As this is a first-in-human safety study of ONL1204, the first patient in the first cohort will receive the lowest dose of ONL1204. After this patient completes Visit 5 (14 +4 days post-surgery) and a safety review committee reviews the data, the remainder of the patients in that cohort will be enrolled. After all patients in the cohort have completed Visit 5, the SRC will review the available safety data to determine if dose

limiting toxicity exists that prohibits enrolling the next higher dose cohort. This process will be repeated until escalating to the top dose.

The following doses will be evaluated: $25 \ \mu g$, $50 \ \mu g$, $100 \ \mu g$, and $200 \ \mu g$ ONL1204. ONL1204 is available in vials with concentrations of 0.5 mg/mL and 2 mg/mL. Therefore, a volume of 0.05 or 0.1 mL will be injected into the study eye.

Patient participation will be approximately 24 weeks (6 months): a single injection treatment and 24 weeks of follow-up.

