9.1 Statistical Design

9.1.1 Statistical Hypotheses

No hypothesis will be formally tested in this study.

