9.1.2 Sample Size

The number of patients to be enrolled has been selected to provide information for this Phase 1 study. No formal sample size calculation is provided given the pilot nature of this study.

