9.3.1 Safety Analyses

All safety analyses will be based on the Safety Population. Safety will be assessed through adverse event reporting, clinical evaluations including BCVA, ophthalmic imaging, and clinical laboratory evaluation.

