9.3.1.5 Ophthalmic Imaging

Ophthalmic imaging will be conducted at the last study visit (exit/early termination), and these results will be measures of interest. Parameters will be summarized using descriptive statistics by treatment group. Ophthalmic Imaging assessments will be split between the study eye and fellow eye.

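### SAP 13.1.14 reports a second set of SD-OCT results, including every layer-specific outer-retina measure, only if an undefined expert review finds them worth including

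*SAP*

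**What the plan says.** Protocol 9.3.1 makes imaging one of the means of assessing safety: "Safety will be assessed through adverse event reporting, clinical evaluations including BCVA, ophthalmic imaging, and clinical laboratory evaluation". Protocol 9.3.1.5 says of imaging: "Parameters will be summarized using descriptive statistics by treatment group", split by study and fellow eye. It names no OCT parameter and refers to the last visit. SAP 13 lists ophthalmic imaging among the safety endpoints to be summarised descriptively on the safety population.

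SAP 13.1.14 then defines two sets of SD-OCT results.

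- **First set.** Seven continuous and five categorical parameters are to be summarised, and the sponsor presents the results in an addendum to the main output. The set includes foveal subretinal-fluid thickness, intraretinal fluid (cystoid macular oedema) and an overall Anomaly item.
- **Second set.** Three layer boundaries, five fluid presence or location items, and the details of any anomaly are also to be obtained. For the continuous results the SAP says: "These results may be analyzed and reviewed, with or without descriptive statistics, internally". A parallel sentence covers the categorical ones. The results are then "included in the addendum to the tables, listings, and figures report only if deemed pertinent and potentially informative by expert review".

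SAP 15 declares no change to the planned analysis. The table and listing indexes in SAP 18 and 19, as shown, contain no SD-OCT entry.

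**The concern.** The second-set condition acts on results that already exist: the text speaks of results from analyses, which then enter the addendum or do not. In an open-label study, with no named reviewer and no criteria, the content of the final record can depend on what the data show. An unwelcome pattern could be left out as uninformative, and a welcome one could be included as pertinent.

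The affected measures are not peripheral. Protocol 1.4.1 lists "Retinal cell death" among the potential risks of the product, and the protocol's rationale rests on photoreceptor loss. Within the SAP's OCT list, the boundary measures in the second set are the only ones that separate the outer retina from the rest. Total thickness and volume mix outer retina, inner retina and fluid. At stake is whether a later reader of the study report can see the outer-retina findings for each dose, whichever way they point.

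**Working it through.** The plan states no figure to reproduce, so the check is a comparison of texts and a count.

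**1. Is the second set within the scope of the imaging commitment?** Protocol 9.3.1 and 9.3.1.5 cover ophthalmic imaging in general. SAP 13 repeats this, and 13.1.14 sits inside the SAP's safety section. SD-OCT is in the Schedule of Assessments (Protocol Table 4-1). So yes, under a general commitment that names no parameter.

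**2. What is committed and what is conditional?** ONL in the boundary names is read here as the outer nuclear layer.

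| Content | Committed (first set) | Conditional (second set) |
|---|---|---|
| Outer-retina boundaries (inner ONL border to Bruch's; ELM to Bruch's) | 0 | 2 |
| Inner-retina boundary (ILM to inner ONL border) | 0 | 1 |
| Fluid items | 2 (foveal subretinal thickness; intraretinal fluid) | 5 (2 intraretinal, 3 subretinal) |
| Anomaly | 1 (overall item) | 1 (details by type) |
| Other thickness, volume, traction and membrane items | 9 | 0 |
| Total bullets | 12 | 9 |

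**3. Share that is conditional.** By bullet: 9 / (12 + 9) = 9 / 21 = 43%. Each boundary is reported at 1, 3 and 6 mm plus a central 1 mm volume, so expanding the boundaries gives 3 × 4 = 12 continuous results plus 6 categorical items = 18, and 18 / (12 + 18) = 60%. Of those 12 continuous results, 2 × 4 = 8 are outer-retina and 4 are inner-retina. The percentage depends on the counting rule. The outer-retina row does not: nothing is committed under either count.

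**4. Is there a fallback listing?** SAP 19 lists colour fundus photography (16.2.11.4), autofluorescence (16.2.11.5) and even the optional B-scan (16.2.4.5), but not SD-OCT. SAP 3 promises listings of all eCRF data, and the documents do not say whether OCT gradings are recorded on the eCRF. Protocol 9.3.1.8 gives residual safety data a listing by treatment group, with further summaries optional. The second OCT set is guaranteed neither.

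**5. How many patients are involved?** "Sixteen patients will be enrolled in 4 ascending dose groups": 16 / 4 = 4 per dose. At that size one or two eyes can be the whole signal, so a complete by-patient listing is the main safeguard.

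**The case against.** The strongest reply is that this is a small, uncontrolled Phase 1 study in which "No hypothesis will be formally tested in this study", so a second descriptive tier is a reasonable choice. Protocol 9.3.1.5 names no OCT parameter, and the SAP uses no pre-injection OCT result, which limits interpretation further. OCT is missing from SAP 18 and 19 because the SAP places it in an addendum. This stands as a defence of optional analysis. It does not defend disclosure that depends on a review of the results.

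A reader might also infer more than the documents support:

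- **That the sponsor decides.** The SAP says expert review. Sponsor control is a plausible inference, because the analysis is internal and the sponsor prepares the addendum, but it is not stated. The criterion could also be meant to cover data usability.
- **That dose decisions would be made without these data.** Protocol 10.2 has the safety review committee consider imaging data, and SAP 13.1.14 does not restrict that. Internal review leaves the sponsor able to see the second set when choosing Phase 2 doses. No dose-limiting criterion in Protocol 4.2.1 is an OCT measure.
- **That subretinal fluid or RPE change would go unreported.** Foveal subretinal-fluid thickness is committed. A case of RPE atrophy should appear under the overall Anomaly item, though perhaps not by type. Protocol 7.11 requires clinically relevant deterioration to be recorded as an adverse event, and SAP 13.1.8 summarises the macula, vessels and periphery.
- **That a protocol-specified parameter was dropped.** None was named. The SAP narrows a general commitment, so the SAP 15 entry is incomplete at most and not clearly false.

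**Conclusion.** The point holds in this limited form. SAP 13.1.14 makes reporting of part of the safety imaging conditional on an undefined review of the results, and that part includes every layer-specific outer-retina OCT measure and the breakdown of anomalies by type. Protocol 9.3.1 and 9.3.1.5 and SAP 13 contain no such filter. The consequence is a risk of selective reporting in the final study record. No effect on dose escalation, dose selection or committee oversight is shown.

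By bullet count 9 of 21 items are affected; the more useful measure is that 0 of the 2 outer-retina boundaries are committed. The conclusion assumes that the condition governs only the second set. The SAP's wording could be stretched to cover the first set, but the separate sentence committing the first set to the addendum makes that unlikely. It also assumes that no SD-OCT output is specified in SAP section 20, which is not in the text available. If OCT gradings are recorded on the eCRF, the general listing rule would already close part of the gap. This is a cheap improvement and not a threat to the study's primary objective.

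**What to change.** In SAP 13.1.14:

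- Delete the condition that second-set results are "included in the addendum to the tables, listings, and figures report only if deemed pertinent and potentially informative by expert review".
- Commit to a by-patient listing, in the addendum and regardless of results, of every second-set parameter obtained.
- Add a descriptive by-cohort summary of at least the two outer-retina boundary thicknesses and of the anomaly types (RPE atrophy, outer retinal lucency). The remaining second-set items can stay as listings with optional summaries, in line with Protocol 9.3.1.8.

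In SAP 18 and 19, add the SD-OCT outputs or cross-reference the addendum.

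The measurements are already planned, so no new visit, scan or reading is needed. The cost is a SAP wording change, a few descriptive outputs and a slightly longer addendum.
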